9.4. Lung Function

Measurements will include oxygen saturation (SpO_2) via pulse oximetry and Partial pressure of oxygen and carbon dioxide in arterial blood (PaO_2 and $PaCO_2$). The pH, lactate and bicarbonate levels of ABGs will also be documented when ABGs are assessed as well as the base excess/deficit if available. Oxygen requirement (FiO_2) will be collected and documented at the same time as ABG collection.

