12.6. Appendix 6: Protocol Amendment History

The Protocol Amendment Summary of Changes Table for the current amendment is located directly before the Table of Contents.

Protocol Amendment 2 (27-Nov-2017)

Overall Rationale for the Amendment: In this amendment, an exploratory outcome and emergency consent have been added. In addition, clarification was added throughout the protocol.

Section # and Name	Description of Change	Brief Rationale
2. Schedule of Assessments	Added Sequential Organ Failure (SOFA) score	Clarification that SOFA will be calculated on a daily basis. All components needed to calculate the score were already being collected.
2. Schedule of Assessments	The following language was added in Footnote 2 of Schedule of Assessments: Other measurements (e.g. ventilator settings) to be prioritized as per investigator for patient care.	The timing of exploratory outcomes can be prioritized by investigators in the best interest of patients as part of standard of care.
2. Schedule of Assessments	A note was added that SAPS II will only be measured at screening.	The timing of the assessment was clarified.
2. Schedule of Assessments 4. Objectives and Endpoints 9.5.5 General management status	Added Participant Management which includes use of ECMO and ECCO2R.	Sites have recently included use of ECMO and ECCO2R as part of patient's standard management. The use needs to be documented in case of interaction with outcomes.
2. Schedule of Assessments 4. Objectives and Endpoints 9.3 Ventilator settings	Static compliance was added as a measurement that will be collected with other ventilator settings.	It had previously been missed; static compliance is a standard measure read from the ventilator.
2. Schedule of assessments 4. Objectives and Endpoints 9.4 Lung Function	pH and base excess were added as measurements that will be collected with other lung function measurements.	These measurements had previously been missed. 
 • pH is a standard measure automatically calculated from blood gas analysis. • Base excess is a standard blood gas analysis. Depending on the base status of the patient a base

Section # and Name	Description of Change	Brief Rationale
		excess result may be collected rather than base deficit.

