Ventilator settings	X ³	X	X	X		Includes tidal volume, respiratory rates, static respiratory compliance, level of positive end expiratory pressure (PEEP), peak and plateau ventilator pressures, mean airway pressure and driving pressure. Measurements to be taken at intubation and at the time of each echocardiogram (\pm 30 mins) ² .
Lung function and blood gas measures	X ³	X	X	X		Oxygen saturation (SaO ₂) via pulse oximetry. Arterial Blood Gases (ABGs) measuring partial pressure of oxygen and carbon dioxide (PaO ₂ and PaCO ₂). ⁴ Oxygen requirement (FiO ₂) should be documented at the same time point. pH, lactate and bicarbonate levels and base excess or deficit when available should also be documented when ABGs are assessed. Measurements to be taken at intubation and at the time of each echocardiogram (\pm 30 mins) ² .

Procedure	Study Period					Notes
	Screening ¹	Day 1	Day 2	Day 3	Up to day 28	
Electrical Impedance Tomography	X	X	X	X		Measurements to be taken at intubation and at the time of each echocardiogram when available (± 2 hours) ² .
Serious Adverse Event (SAE) Review	<=====>					SAEs will only be collected during the 3 day observation period or until participant withdrawal, whichever is sooner.
Concomitant medication review	<=====>					Only specified prescription medication (name, start and end dates required) as described in Section 7.1 of the protocol. Vasopressor use to be documented for each time point of echocardiography.
Intensive Care Unit (ICU) length of stay		<=====>				Will be recorded daily up to 28 days.
Ventilator free days		<=====>				Will be recorded daily up to 28 days; however, follow up is not necessary beyond hospital discharge.
In hospital mortality		<=====>				Will be recorded daily up to 28 days; however, follow up is not necessary beyond hospital discharge.
Biomarkers						
Blood sample for renin-angiotensin system (RAS) biomarkers		X	X	X		Blood samples to be taken at the same time as echocardiography (± 30 mins) ² .
Blood sample for biomarkers		X	X	X		Blood samples to be taken at the same time as echocardiography (± 30 mins) ² .

1. Screening may be considered part of Day 1.
2. When multiple measurements are to be taken at the same time in relation to echocardiography, blood sampling for RAS peptides should be given priority. Other measurements (e.g. ventilator settings) to be prioritized as per investigator for patient care.
3. Will be recorded at the time of intubation if available.

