Time	PAO2	Partial pressure of arterial O2 (mmHg) (Continuous)	DMDATA.LAB (Where VISITNUM in (10,20,30,40) & LBREFID ^=SOFA & LBTESTCD=PAO2_BLP) For each subject select the most recent non-missing value from visitnum 10,20 (and set result to have visitnum=20) prior to merging by subject and visitnum Select LBORRESN
Time	PAO2DM	DateTime of PAO2 Sample (DateTime)	DMDATA.LAB (Where VISITNUM in (10,20,30,40) & LBREFID ^=SOFA & LBTESTCD=PAO2_BLP) For each subject select the most recent non-missing LBORRESN value from visitnum 10,20 (and set result to have visitnum=20) prior to merging by subject and visitnum Combine LBDT and LBACTM into a single datetime formatted variable

Type	Variable Name	Details	Suggestions for derivation / data source
Time	PACO2	Carbon dioxide partial pressure (mmHg) (Continuous)	DMDATA.LAB (Where VISITNUM in (10,20,30,40) & LBREFID ^=SOFA & LBTESTCD=PCO2_BLP) For each subject select the most recent non-missing value from visitnum 10,20 (and set result to have visitnum=20) prior to merging by subject and visitnum Select LBORRESN
Time	LA ^T	Serum Lactate (mmol/L) (Continuous)	DMDATA.LAB (Where VISITNUM in (10,20,30,40) & LBREFID ^=SOFA & LBTESTCD=LACT_PLC) For each subject select the most recent non-missing value from visitnum 10,20 (and set result to have visitnum=20) prior to merging by subject and visitnum Select LBORRESN
Time	HC03	Serum Bicarbonate (mEq/L) (Continuous)	DMDATA.LAB (Where VISITNUM in (10,20,30,40) & LBREFID ^=SOFA & LBTESTCD=HC03_PLC) For each subject select the most recent non-missing value from visitnum 10,20 (and set result to have visitnum=20) prior to merging by subject and visitnum Select LBORRESN
Time	PH	Blood pH (Continuous)	DMDATA.LAB (Where VISITNUM in (10,20,30,40) & LBREFID ^=SOFA & LBTESTCD=PH_BLG) For each subject select the most recent non-missing value from visitnum 10,20 (and set result to have visitnum=20) prior to merging by subject and visitnum Select LBORRESN
Time	BASEXA	Base excess (arterial whole blood) (mEq/L) (Continuous)	DMDATA.LAB (Where VISITNUM in (10,20,30,40) & LBREFID ^=SOFA & LBTESTCD=BASEXA_BLC) For each subject select the most recent non-missing value from visitnum 10,20 (and set result to have visitnum=20) prior to merging by subject and visitnum Select LBORRESN

Type	Variable Name	Details	Suggestions for derivation / data source

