Time	BDEFA	Base deficit (arterial whole blood) (mEq/L) (Continuous)	DMDATA.LAB (Where VISITNUM in (10,20,30,40) & LBREFID ^=SOFA & LBTESTCD=BDEFA_BLC) For each subject select the most recent non-missing value from visitnum 10,20 (and set result to have visitnum=20) prior to merging by subject and visitnum Select LBORRESN
Time	TROPI	Troponin I (UG/L) (Continuous)	DMDATA.LAB (Where VISITNUM in (10,20,30,40) & LBREFID ^=SOFA & LBTESTCD=TROPI_PLC) For each subject select the most recent non-missing value from visitnum 10,20 (and set result to have visitnum=20) prior to merging by subject and visitnum Select LBORRESN
Time	TROPT	Troponin T (UG/L) (Continuous)	DMDATA.LAB (Where VISITNUM in (10,20,30,40) & LBREFID ^=SOFA & LBTESTCD=TROPT_PLC) For each subject select the most recent non-missing value from visitnum 10,20 (and set result to have visitnum=20) prior to merging by subject and visitnum Select LBORRESN
Time	PFSOFA	PaO2/FiO2 entered onto SOFA form (Continuous)	DMDATA.LAB (Where VISITNUM in (10,20,30,40) & LBREFID =SOFA & LBTESTCD=PAO2FI_BLQ) For each subject select the most recent non-missing value from visitnum 10,20 (and set result to have visitnum=20) prior to merging by subject and visitnum Select LBORRESN
Time	FIO2	Fraction of Inspired Oxygen (%) (Continuous)	DMDATA.FAPR (Where VISITNUM in (20,30,40) & FPRSTCD=FPRAW005) Select FPRORSN. Match on subjid and visitnum

Type	Variable Name	Details	Suggestions for derivation / data source
Time	FIO2DM	DateTime of FIO2 Sample (DateTime)	DMDATA.FAPR (Where VISITNUM in (20,30,40) & FPRSTCD=FPRAW005) Combine FPRDT and FPRTM into a single datetime formatted variable Match on subjid and visitnum
Time	PFDIFF	Difference between PaO2 and FiO2 Sampling occasions (mins)	(PAO2DM - FIO2DM) converted into minutes
Time	PFECRF	PaO2/FiO2 derived (Continuous)	PAO2 / (FIO2 / 100)
Time	PFECRF30	PaO2/FiO2 (sampling within ± 30 mins) (Continuous)	Select PFECRF if $ABS(PFDIFF) \leq 30$; set to missing otherwise
Time	FPRBH001	Static Respiratory System Compliance (mL/cm H ₂ O) (Continuous)	DMDATA.FAPR (Where VISITNUM in (20,30,40) & FPRSTCD= FPRBH001) Select FPRORSN. Match on subjid and visitnum
Time	FPRBH003	Pressure Support Ventilation (Binary Y/N)	DMDATA.FAPR (Where VISITNUM in (20,30,40) & FPRSTCD= FPRBH003) Match on subjid and visitnum Set Y if FPRORSCD=ZZY Set N otherwise
Time	FPRAB001	Tidal Volume (mL) (Continuous)	DMDATA.FAPR (Where VISITNUM in (20,30,40) & FPRSTCD= FPRAB001) Select FPRORSN. Match on subjid and visitnum

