1.7.	Safety	DM1	Summary of Demographic Characteristics by PCD/ACP status	
ICH E3, FDAAA, EudraCT
 
Instead of the set of treatment variables (columns) please use "No PCD/ACP" and "Any PCD/ACP" and "All Participants" as columns to group the subjects
 
As well as the standard set of demography items (Sex, Age, Age Group, Height, Weight, BMI) please also include the following Disease specific baseline variables (with units if applicable) to facilitate manuscript publication (mixture of continuous and categorical variables)
 
Baseline should be the earliest non-missing value from SCREENING or DAY 1 visits. Do not display values from Days 2 or 3 (if multiple timepoints are available for an item)
 
SAPSII, SOFA, PaO2/FiO2 (from SOFA form), PaO2, FiO2, PaCO2, Oxygenation Index, Reason for Intubation (use the mapped variable not free text results), Proned, Receiving Inhaled Nitric Oxide, "Managed with Vasopressors, inotropes or other vasoactive agents", ECMO, ECCO2R, Global Inhomogeneity Index, SpO2, Serum Lactate, Serum Bicarbonate, pH, Base excess (arterial whole blood), Base deficit (arterial whole blood), Central Venous Pressure, Static respiratory system compliance, Respiratory rate (not from vitals but from FAPR), Pressure support (Y/N), Tidal Volume, PEEP, Peak Pressure, Plateau Pressure, Mean Airway Pressure, Driving Pressure, In-hospital Mortality (Y/N/Unknown)
 
Note: Summarise with n, Median, Lower and Upper quartiles, Min and Max:
 
Length of stay in ICU, Length of stay in hospital, Ventilation free days
	SAC 2

Study Population Tables					
No.	Population	IDSL / Example Shell	Title	Programming Notes	Deliverable [Priority]
1.8.	Safety	DM11	Summary of Age Ranges	EudraCT	SAC 2
Prior and Concomitant Medications					
1.9.	Safety	MH4	Summary of Current Medical Conditions	ICH E3	SAC 2
1.10.	Safety	MH4	Summary of Past Medical Conditions	ICH E3	SAC 2
1.11.	Safety	CM1	Summary of Concomitant Medications	ICH E3 Exclude the SOFA related records	SAC 2

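### Base excess and base deficit record one signed quantity, but SAP Tables 9 and 1.7 carry them as two unmerged variables, so each baseline row can describe a sign-selected subset (low impact)

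*SAP*

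**What the plan says.** **Collection.** The schedule (protocol section 2, repeated in SAP 10.2.1) asks that "base excess or deficit when available should also be documented when ABGs are assessed". Protocol 9.4 treats it as a single item, "as well as the base excess/deficit if available". The Amendment 2 rationale in protocol Appendix 6 explains why base excess was added: "Depending on the base status of the patient a base" ... "excess result may be collected rather than base deficit" (one sentence, split by a table break). Blood gases are due at intubation, if available, and at each echocardiogram, so a participant can have both a Screening and a Day 1 result.

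**Covariate dataset.** SAP Table 9 builds BASEXA, "Base excess (arterial whole blood) (mEq/L) (Continuous", and BDEFA, "Base deficit (arterial whole blood) (mEq/L) (Continuous", from two different laboratory test codes. Each carries its own Day 1 rule: "For each subject select the most recent non-missing value from visitnum 10,20 (and set result to have visitnum=20) prior to merging by subject and visitnum".

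**Reporting.** Table 1.7 summarises baseline characteristics in columns for no PCD/ACP, any PCD/ACP and all participants. Its list includes "Base excess (arterial whole blood), Base deficit (arterial whole blood" as two items. Its baseline rule takes the first available result from Screening or Day 1. Listing 6 uses the same variables.

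**The concern.** Base deficit is base excess with the sign reversed. If a blood gas fills one field or the other according to sign, splitting the fields conditions each summary on the outcome being summarised. The Table 1.7 columns then compare selected subsets, and neither row gives a group's acid-base status.

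The selection rules add a second problem. They run within a test code, so a newer excess cannot displace an older deficit stored under a different code.

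At stake is the validity of two rows in a descriptive table that is still planned after early termination, and whose disease-specific items were added with publication in mind.

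**Working it through.** The plan states no figure on this point, so there is none to reproduce. The check has two parts.

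**1. Trace of the rules.** Apply Table 9 (latest available) and Table 1.7 (first available) to each test code separately.

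| Screening | Day 1 | Table 9 Day 1 record | Table 1.7 rows entered |
|---|---|---|---|
| deficit 4 | excess 2 | BDEFA = 4 and BASEXA = 2 | both |
| excess 3 | deficit 1 | BASEXA = 3 and BDEFA = 1 | both |
| deficit 4 | deficit 2 | BDEFA = 2 only | deficit only |

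In the first line the participant's earliest signed value is -4 and the latest is +2. The stored record holds both values, from two visits, with nothing to show which is current.

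**2. Illustration of size.** All inputs are assumptions, since the documents give no distribution for base excess. Let signed base excess be normal with mean μ and SD σ, with every negative result entered as a positive deficit. Put z = -μ/σ. Then:

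- share in the deficit field = Φ(z)
- mean of the deficit row = -μ + σφ(z)/Φ(z)
- mean of the excess row = μ + σφ(z)/(1 - Φ(z))

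Take σ = 6 mEq/L and group means -5 and 0.

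- Mean -5: z = 0.833, φ = 0.2819, Φ = 0.7977. Deficit row: 5 + 6 × 0.2819/0.7977 = 7.12, on 80% of participants. Excess row: -5 + 6 × 0.2819/0.2023 = 3.36, on 20%.
- Mean 0: z = 0, φ = 0.3989, Φ = 0.5. Both rows: 6 × 0.3989/0.5 = 4.79, on 50% each.
- Row differences: 7.12 - 4.79 = 2.33 for deficit and 3.36 - 4.79 = -1.43 for excess. The true signed difference is 5.0.

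A second setting, simulated with σ = 5 and group means -5 and -1 (true difference 4), gives deficit rows of 6.43 and 4.39 (difference 2.04) and excess rows of 2.63 and 3.65 (difference -1.02).

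Over assumed single-group means from -6 to +3 with σ = 5, the excess row holds 12% to 73% of participants. If the gas is measured at both visits, with a between-visit correlation of 0.5 or 0.8, 10% to 33% of Day 1 records hold both values.

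**Can the signed mean be recovered from the two rows?** With no sign changers, yes.

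- First setting: -0.7977 × 7.12 + 0.2023 × 3.36 = -5.68 + 0.68 = -5.00 in one group, and -0.5 × 4.79 + 0.5 × 4.79 = 0 in the other.
- Second setting: -0.84 × 6.43 + 0.16 × 2.63 = -4.98, and -0.58 × 4.39 + 0.42 × 3.65 = -1.01.

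Sign changers blur this because they count twice. The first participant in the table contributes 4 to the deficit row and 2 to the excess row, which recombine to (-4 + 2)/2 = -1, although the first available value is -4.

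**The case against.** Several points on the other side stand.

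- **Covariates.** A reader might infer that patients would be dropped from the model because each variable is blank for the other sign. The documents do not support this. Neither variable is among the 14 potential covariates in SAP 7.1.1, and the same section says covariate exploration may not happen at all. Table 9 is titled as suggested metadata open to modification, and keeping both source codes in it loses no information.
- **Sign.** A reader might also infer that each row strictly contains one sign. No sign convention is stated. The amendment rationale says only that an excess may be collected in place of a deficit. A site entering negative base excess values would break the split. The SAP has no rule for that case either, and a row would then mix conventions.
- **Hidden difference.** It is tempting to say that a real group difference would be concealed. The recombination above shows that n and mean from both rows nearly give it back. In the first setting the counts and both row means also point the same way: more deficits, larger deficits, smaller excesses. Table 1.7 also reports pH, bicarbonate and lactate.
- **Stakes.** Base excess is not a named endpoint, no formal hypotheses are tested (SAP 2.4), and Table 1.7 is a second-priority descriptive output.

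What the objection does not remove is that, followed as written, the plan prints two rows that each need the other to be interpretable. It also lets one participant enter both, and stores a Day 1 record drawn from two visits.

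**Conclusion.** The point holds, with low impact. The documents describe one quantity recorded in alternative fields, and no step in the SAP rejoins them. The either/or split of Table 1.7 depends on sites having used the fields by sign, which the collection text suggests but does not guarantee. The double entry and mixed-visit record need a change of field between Screening and Day 1, and results at both visits.

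Under the assumed distributions, a true difference of 5.0 mEq/L appears as 2.3 and -1.4, and one of 4 as about 2.0 and -1.0. These are illustrations, not estimates for this study. The effect is confined to a descriptive baseline table and an optional pool of variables. The primary model and the listed covariates are unaffected.

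**What to change.** 1. Before deriving anything, tabulate the sign of the recorded values in each field by site, and settle how each field was used. Without this check, negating a deficit that was already entered as a negative number would turn it into a false excess.
2. In Table 9, derive one signed base excess per blood gas: the recorded excess, or the deficit converted to a negative value. Take it from one sample at one visit and time.
3. Apply the existing Screening/Day 1 rules (latest for ALLCVTS, earliest for Table 1.7) to that single variable.
4. Replace the two Table 1.7 rows with one. Use the same variable if acid-base status is ever screened as a covariate. Listing 6 may keep the values as recorded.

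The cost is a short data check, one derivation line and one merged row. No new data are needed.

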10.7. Appendix 7: Reporting Standards for Missing Data

10.7.1. Premature Withdrawals

Element	Reporting Detail
General	
 Subject study completion (i.e. as specified in the protocol) was defined as having completed the Day 3 assessments as shown in the SoA. Withdrawn subjects may be replaced in the study. All available data from participants who were withdrawn from the study will be listed and all available planned data will be included in summary tables and figures, unless otherwise specified (e.g. because they withdrew consent as detailed in the study protocol). Withdrawal visits will be slotted as per Appendix 3: Assessment Windows or will be summarised as withdrawal visits.

10.7.2. Handling of Missing Data

Element	Reporting Detail
General	
 Missing data occurs when any requested data is not provided, leading to blank fields on the collection instrument: 
 These data will be indicated by the use of a “blank” in participant listing displays. Unless all data for a specific visit are missing in which case the data is excluded from the table. Answers such as “Not applicable” and “Not evaluable” are not considered to be missing data and should be displayed as such.
Outliers	
 Any participants excluded from the summaries and/or statistical analyses will be documented along with the reason for exclusion in the clinical study report.
Missing Categorical Covariates	
 In the statistical models of RAS peptides as predictors of measures of RV function (and other associated models), a number of categorical covariates (e.g. sex, prior history of RAS modulators, type of echocardiogram, use of vasopressors, proning status, use of nitric oxide) may be required. The following rules should be applied to variables that are to be included in the final statistical model: 
 In the unlikely event that sex is not recorded for a participant, then data from that participant will not be included. For prior history of RAS modulators, a participant is assumed not to have had such a history unless explicitly reported otherwise. For the other variables listed above, which are recorded on each study day, the following imputation algorithm should be applied for missing values: 
 If the same variable is not missing on a previous study day (including screening, if applicable), impute the most recent known value. Otherwise, if the same variable is not missing on a subsequent study day, impute the value from the nearest time point after the missing one. Otherwise, keep the value as missing and exclude the participant from the analysis

10.7.2.1. Handling of Missing and Partial Dates/Times

Element	Reporting Detail
General	
 Partial dates will be displayed as captured in participant listing displays.
Adverse	
 The eCRF allows for the possibility of partial dates (i.e., only month and year) to be

Element	Reporting Detail
Events	
recorded for AE start and end dates; that is, the day of the month may be missing. In such a case, the following conventions will be applied for calculating the time to onset and the duration of the event:
 
 ○ Missing Start Day: First of the month will be used unless this is before the start date of study treatment; in this case the study treatment start date will be used and hence the event is considered On-treatment as per Appendix 4: Study Phases and Treatment Emergent Adverse Events. ○ Missing Stop Day: Last day of the month will be used, unless this is after the stop date of study treatment; in this case the study treatment stop date will be used. ● Completely missing start or end dates will remain missing, with no imputation applied. Consequently, time to onset and duration of such events will be missing.
Concomitant Medications/ Medical History	
 ● Partial dates for any concomitant medications recorded in the CRF will be imputed using the following convention: 
 ○ If the partial date is a start date, a '01' will be used for the day and 'Jan' will be used for the month ○ If the partial date is a stop date, a '28/29/30/31' will be used for the day (dependent on the month and year) and 'Dec' will be used for the month. ● The recorded partial date will be displayed in listings.

